5.4 Removal of Subjects from Therapy or Assessment

5.4.1 Discontinuation of Individual Subjects from Treatment

Each subject has the right to withdraw from the study at any time. In addition, the investigator will discontinue a subject from the study at any time if the investigator considers it necessary for any reason including:

- The investigator believes it is in the best interest of the subject;
- The subject's response to therapy is unsatisfactory, as evidenced by progression of disease while on study drug;

- The subject experiences toxicities related to study drug that require more than a 4-week (one cycle) dose interruption of venetoclax or LDAC, in the absence of clinical benefit;
- The subject requires any radiotherapy or alternate chemotherapy during the study period (with the exception of hydroxyurea [allowed in first month only]);
- The occurrence of an adverse event that precludes further LDAC administration;
- Noncompliance with the protocol.
- Treatment failure, defined as failure to achieve CR, CRi, PR, or MLFS.
- The subject becomes pregnant while on study drug.

Treatment will be continued as long as the patient continues to derive clinical benefit or until documented disease progression or develops unacceptable toxicity.

Accordingly, subjects may, in rare occasions, continue treatment after documented disease progression if the investigator believes it is in the best interest of the patient.

Following the final analysis results, the subjects will be unblinded by the Sponsor to the treatment assignment and subjects will be allowed to continue the assigned treatment arm as long as they derive clinical benefit from the treatment in the opinion of the investigator, or until transition to commercial supply is available, or until protocol criteria for discontinuation is met.

The investigator or study site personnel will inform AbbVie prior to discontinuing a subject from the study by contacting the Medical Monitor as identified in Section 7.0. All subjects will be included for analysis of safety data.

In the event that a subject withdraws or is discontinued from the study, the reason(s) for the discontinuation from the study and the primary reason will be recorded and a Final Treatment Visit along with all necessary procedures per [Appendix C](#) (will be performed as soon as possible after discontinuation from the study). The subject would then enter

Post Treatment Follow Up as outlined in Section 5.1.4 and follow all necessary procedures per [Appendix C](#).

At the end of the subject's participation in the study, the calendars/diaries are to be returned to the site and appropriately filed with the subject's source documents for this study.

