- End of Cycle 1 (must be performed within ± 3 days of Cycle 1 Day 28 and resulted prior to the administration of treatment for Cycle 2).
- For subjects with resistant disease at end of Cycle 1 a repeat bone marrow must be performed at the end of Cycle 2 or Cycle 3 based on the hematologic recovery to assess for a response of CR/CRi.

- For subjects with a response of CRi on two successive bone marrow samples, an additional bone marrow aspirate and biopsy must be performed to confirm a CR once peripheral blood count recovery is noted. This is not required for subjects who are unblinded following the final analysis results.
- For all subjects a bone marrow aspirate and biopsy must be performed at end of Cycle 4 and every 3 cycles (\pm 1 week) thereafter. This is not required for subjects who are unblinded following the final analysis results. Bone marrow aspirate and/or biopsy can be completed as per institutional standard of care.
- Upon concern for relapse or progressive disease.
- Final Visit (if no BM collected within the last 6 – 8 weeks. Disease assessment is not required if relapse of disease has already been confirmed.)

A bone marrow aspirate and biopsy must be performed for all subjects during screening to confirm diagnosis and to collect mandatory samples for mandatory biomarker assessments. Historical bone marrow aspirates and biopsies assessed locally to confirm the diagnosis may be used as baseline assessment to satisfy eligibility criteria if they were collected as standard of care within 30 days prior to randomization. During screening, after informed consent is signed, bone marrow aspirates and biopsies may be collected to confirm the diagnosis to satisfy eligibility criteria.

During screening, after informed consent is signed, a bone marrow aspirate must be performed for all subjects to collect samples for mandatory biomarker assessments (*biomarker collections are not applicable to subjects enrolled in China*).

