EFS will be defined as the number of days from randomization to the date of progressive disease, relapse from CR to CRi, treatment failure defined as failure to achieve CR, CRi, PR, or MFLS, or death from any cause. If a specified event does not occur, subjects will be censored at the date of last disease assessment. Data for subjects without any disease assessments performed after randomization will be censored at the date of randomization. The distribution of EFS will be estimated for each treatment arm using Kaplan-Meier methodology and compared between treatment arms using the log-rank test stratified by AML status (secondary, de novo) and age ($18 - < 75, \geq 75$).

Post baseline transfusion independence rate will be calculated as the portion of subjects who achieved transfusion independence post baseline. Transfusion independence is defined as a period of at least 56 days with no transfusion between the first dose of study drug and the last dose of study drug plus 30 days. In addition, the rate of conversion will be calculated as proportion of subjects being post-baseline transfusion independent from baseline transfusion dependence. The transfusion independence rate will be evaluated for 1) RBC and 2) platelets. All randomized subjects will be included to estimate the post-baseline transfusion independence rate.

Post baseline transfusion independence rate will be estimated as the proportion of subjects known to achieve transfusion independence during the evaluation period. Transfusion independence rate will be compared between treatment arms using CMH test stratified by AML status (secondary, de novo) and age ($18 - < 75, \geq 75$). In addition, 95% confidence interval will be constructed for transfusion independence rate.

The rates of conversion from baseline transfusion dependence to post-baseline transfusion independence will be estimated. The conversion rate will be evaluated for 1) RBC and 2) platelets.

The proportion of subjects with complete remission or complete remission with partial hematologic recovery (CR + CRh) by the initiation of Cycle 2 will be calculated. CR + CRh rate by the initiation of Cycle 2 will be compared between treatment arms using CMH test stratified by AML status (secondary, de novo) and age ($18 < 75, \geq 75$). In addition, 95% confidence interval will be constructed for CR + CRh rate by the initiation of Cycle 2.

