10.3.8 Event-free Survival

Event-free Survival (EFS) will be defined as the number of days from randomization to the date of progressive disease, confirmed morphologic relapse from CR or CRi, treatment failure defined as failure to achieve CR, CRi or MLFS after at least 6 cycles of study treatment collected on study drug completion eCRF or death from any cause. The confirmation is required for morphologic relapse (MR). Based on the IWG criteria implemented in the protocol, if the bone marrow blasts are between 5 - 10%, a repeated bone marrow assessment should be conducted to distinguish between bone marrow regeneration and relapse. For MR with bone marrow blast $\leq 10\%$ and followed by a non-PD/non-MR response prior to start of post-treatment therapy, this MR is considered an unconfirmed MR and therefore, the subject is still considered to be a responder.

If the specified event does not occur, subjects will be censored. The detailed censoring rule is described in [Table 4](#). Data for subjects without any disease assessments performed after randomization will be censored at the time of randomization.

Table 4. Event/Censor and Corresponding Event/Censor Time for EFS

Situation	Event/Censor	Event Time/Censor Time
PD, confirmed morphologic relapse (MR),* and treatment failure events on or prior to any post-treatment therapy and data cutoff date, whichever is earliest	Event	Earliest PD, MR or treatment failure event date
Death event on or prior to data cutoff date regardless whether it occurred after any post-treatment therapy initiated	Event	Death date
No PD, confirmed MR,* treatment failure, or death events, and without post-treatment therapy initiated on or prior to the data cutoff date	Censor	Last disease assessment date (bone marrow or hematology lab collection date) on or prior to the data cutoff date
No confirmed MR,* PD, or treatment failure on or prior to post-treatment therapy initiated on or prior to the data cutoff date, and no death on or prior to data cutoff	Censor	Start date of post-treatment therapy

* An un-confirmed MR is defined as a MR with bone marrow blast $\leq 10\%$ and followed by non-PD/Non-MR prior to the post-treatment therapy. Otherwise, MR is considered to be a confirmed MR.

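### The SAP's EFS counts treatment failure only after 6 cycles and leaves PR off the response list, while the protocol sets no time point and counts PR as success, so early failures are counted late or censored

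*Protocol*

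**What the plan says.** Three places define treatment failure.

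- **Protocol 5.4.1 (stopping treatment):** "Treatment failure, defined as failure to achieve CR, CRi, PR, or MLFS". No cycle or date is attached. The list it belongs to is discretionary: "the investigator will discontinue a subject from the study at any time if the investigator considers it necessary for any reason including".
- **Protocol 8.1.4.2 (EFS):** "treatment failure defined as failure to achieve CR, CRi, PR, or MFLS". The responses are the same (MFLS is evidently MLFS), and again there is no time point.
- **SAP 10.3.8 (EFS):** "failure to achieve CR, CRi or MLFS after at least 6 cycles of study treatment collected on study drug completion eCRF". A minimum of 6 cycles appears and PR is no longer listed.

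SAP Table 4 then assigns events and censoring. PD, confirmed relapse or treatment failure before post-treatment therapy is an event. So is a "Death event on or prior to data cutoff date regardless whether it occurred after any post-treatment therapy initiated". A subject with none of these is censored at the start of post-treatment therapy if it was given (the row requires "post-treatment therapy initiated on or prior to the data cutoff date, and no death on or prior to data cutoff"), and otherwise at the last disease assessment.

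**The concern.** The protocol and the SAP define the same component of the same endpoint differently, in both timing and response list. The SAP is written to Amendment 4, and the changes listed for the later amendment do not touch the EFS definition, so this is not a difference between superseded and current text.

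Early failure is foreseeable. Marrow is examined at the end of Cycle 1, and Protocol 5.3.1.1 adds: "For subjects with resistant disease at end of Cycle 1 a repeat bone marrow must be performed" at the end of Cycle 2 or 3. Resistant disease is not PD. In Protocol 5.3.3, PD needs a rise in marrow or peripheral blasts, marrow blasts persistently above 70% for at least 3 months, or new extramedullary disease. A subject can therefore be stopped for non-response well before Cycle 6 without any other EFS event. Protocol 5.1.4 then follows subjects who stop with resistant disease by survival calls, so later PD may go undocumented.

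At stake is an endpoint that is a stated secondary objective, is tested under alpha control in both regional sequences, and is repeated on IRC data. Treatment given because the first regimen failed carries prognostic information, so censoring at its start is unlikely to be independent of outcome.

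**Working it through.** **1. The plan's own figure.** EFS has no stated event count or power. The only sizing is for OS: 133 deaths, 90% power, HR 0.545, 2:1 allocation, two-sided 0.05. A fixed design needs (1.960 + 1.282)² / [(2/9) × (ln 0.545)²] = 128.3, so 129 deaths. With the Lan-DeMets O'Brien-Fleming interim at 100 of 133 deaths, 131 deaths give 90.0% power and 133 give 90.5%. The one-sided boundaries come out at 0.0097 and 0.0221, against 0.010 and 0.022 in SAP Table 1. The OS assumptions therefore reproduce, and they are used below only to give scale.

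**2. Path of an early failure through SAP Table 4.** Take a subject stopped for failure before 6 cycles, with no PD or confirmed relapse before post-treatment therapy.

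| Status at cutoff | Protocol 8.1.4.2 | SAP Table 4 |
|---|---|---|
| Died | Event at failure | Event at death |
| Alive, other therapy started | Event at failure | Censored at start of that therapy |
| Alive, no other therapy | Event at failure | Censored at last disease assessment |

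The PR difference runs the other way: a subject with PR only after 6 cycles is a failure in the SAP and not in the protocol.

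**3. Where 6 cycles falls.** 6 × 28 = 168 days, or 5.5 months. With exponential survival at the planned medians (6 and 11 months), 1 − 2^(−5.52/6) = 47% of control and 1 − 2^(−5.52/11) = 29% of venetoclax subjects would have died by then. At the final analysis 133/210 = 63% of all subjects have died.

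**4. Upper bound and a more realistic split.** For every 10% of an arm stopped early for failure, 0.10 × 70 = 7 control or 0.10 × 140 = 14 venetoclax subjects are affected. All of them are censored only if none dies or has PD. Suppose instead that they die at their arm's planned rate and have no PD. The share still alive f months after stopping is 2^(−f/median).

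| Months from stopping to cutoff | Control censored | Venetoclax censored |
|---|---|---|
| 6 | 50%, 3.5 of 7 | 69%, 9.6 of 14 |
| 12 | 25%, 1.8 of 7 | 47%, 6.6 of 14 |
| 18 | 12.5%, 0.9 of 7 | 32%, 4.5 of 14 |

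The others become events at death. If early failures die faster than their arm's average, fewer are censored.

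**5. Direction between arms.** A large-sample simulation was run on assumed inputs, none of them from the documents:

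- failure stops between 0.92 and 3.68 months, with new therapy 0.25 to 1 month later;
- cutoff 6 to 18 months after randomization;
- median OS of failures 6 months in both arms;
- for the other subjects, median OS of 10 (control) and 15 (venetoclax) months and median relapse times of 8 and 12 months;
- no PR effect.

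With early failure in 40% of control and 20% of venetoclax subjects, the EFS hazard ratio moves from about 0.61 (failure counted when it happens) to about 0.69 (Table 4). With 50% in each arm it moves from about 0.80 to about 0.78. The sign depends on how failures split between arms.

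**The case against.** A reader might infer that subjects stopped early for failure are simply censored instead of counted. Table 4 does not support that. Every death by cutoff is an event, including deaths after other therapy, and the censoring row applies only to subjects alive at cutoff. Late counting still lengthens EFS for these subjects relative to the protocol, but it is a weaker effect than removing them.

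A reader might also infer that the SAP flatters venetoclax, or that EFS is inflated overall. Neither follows. Omitting PR shortens EFS. The protocol's background rates (CR + CRi about 11% on LDAC in Section 3.2; 78% of 18 subjects on the combination in Section 3.0) would suggest more early failure in control, in which case the late counting would work against venetoclax. The trial's own split by arm is not in the documents.

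It is also fair to say that a discretionary stopping rule, a marrow schedule and an endpoint definition need not share a time point. That stands: the direct conflict is between the two EFS definitions. Finally, the failure data come from the study drug completion form, whose content is not shown. If that form itself applies the 6-cycle criterion, earlier failures may not be identifiable from it.

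None of this removes the difference between Protocol 8.1.4.2 and SAP 10.3.8.

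**Conclusion.** The point holds as an inconsistency in the EFS definition with a real consequence for the analysis. Subjects stopped for failure before 6 cycles, without PD or confirmed relapse, have no failure event in the SAP: they are counted late at death, or censored, likely informatively, if alive at cutoff. PR-only subjects after 6 cycles are classified in opposite ways by the two documents.

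The size cannot be fixed from the documents. The 7 and 14 per 10% of an arm are upper bounds on censoring. The 0.9 to 3.5 and 4.5 to 9.6 rest on exponential survival at the planned OS medians, no PD, and 6 to 18 months from stopping to cutoff. The net direction between arms is unknown.

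The reach is limited. OS and the endpoints ranked above EFS are unaffected. EFS is 14th in SAP Table 7 and 16th in Table 8, last apart from subgroup endpoints that may be moved below it.

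**What to change.** Reconcile Protocol 8.1.4.2 and SAP 10.3.8: one response list, with PR explicitly in or out, and one stated rule on timing. In EFS, count study-drug discontinuation recorded as treatment failure before 6 cycles as an event at its date, at least as a prespecified sensitivity analysis beside the 6-cycle definition. State which form field supplies the reason and date, and confirm that it captures failures before Cycle 6.

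The current protocol says the final efficacy analysis has been done. If the 6-cycle definition was used there, the remaining option is to report the departure from the protocol definition and add the alternative analysis, labelled as post hoc.

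The cost is wording in two sections and one further EFS run. Median EFS under the alternative becomes shorter, and the event then relies on the investigator's recorded reason for stopping, which is partly a matter of judgement. The stopping rule in Protocol 5.4.1 and the marrow schedule need no change for this purpose; any inconsistency there is for the sponsor to reconcile.

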5.4.2 Discontinuation of Entire Study

AbbVie may terminate this study prematurely, either in its entirety or at any study site, for reasonable cause provided that written notice is submitted in advance of the intended termination. The investigator may also terminate the study at his/her site for reasonable cause, after providing written notice to AbbVie in advance of the intended termination. Advance notice is not required by either party if the study is stopped due to safety concerns. If AbbVie terminates the study for safety reasons, AbbVie will immediately notify the investigator by telephone and subsequently provide written instructions for study termination.

If, in the judgment of the investigator and AbbVie, the continued exposure to the study drug represents a significant risk to subjects, the study will be stopped. The following procedures for discontinuation will be followed:

- If the sponsor has decided to prematurely discontinue the study, the sponsor will promptly notify in writing the investigator as well as regulatory authorities of the decision and give detailed reasons for the discontinuation.
- The investigator must promptly notify the IEC/IRB and give detailed reasons for the discontinuation.

The investigator must promptly notify the enrolled subjects of the premature discontinuation and administer appropriate treatments such as replacement of the treatment regimen, if applicable, by other appropriate regimens.

5.5 Treatments

5.5.1 Treatments Administered

Subjects will take daily venetoclax or placebo orally in the form of tablets. Venetoclax or placebo should be dosed before LDAC on days of LDAC administration. Subjects will self-administer venetoclax or placebo by mouth QD. Tablets must be swallowed whole and must not be broken, chewed, or crushed.

LDAC must be prepared as per the applicable Summary of Product Characteristics (SmPC), package insert or prescribing information and administered subcutaneously by a trained provider meeting local qualifications for administration of subcutaneous cytarabine.

5.5.2 Identity of Investigational Products

Table 5. Identity of Investigational Product

Study Drug	Trademark	Formulation	Route of Administration	Manufacturer
Venetoclax	N/A	100 mg Tablet	Oral	AbbVie
Venetoclax	N/A	50 mg Tablet	Oral	AbbVie
Venetoclax	N/A	10 mg Tablet	Oral	AbbVie
Matching Placebo for Venetoclax (100 mg Tablet)	N/A	0 mg Tablet	Oral	AbbVie
Matching Placebo for Venetoclax (50 mg Tablet)	N/A	0 mg Tablet	Oral	AbbVie
Matching Placebo for Venetoclax (10 mg Tablet)	N/A	0 mg Tablet	Oral	AbbVie
Cytarabine	N/A	100 mg/5 ml vial	SC	Brand/Generic

AbbVie will provide venetoclax, and placebo for venetoclax, and may also provide cytarabine for the study. Sites located in countries where cytarabine is approved for AML may obtain cytarabine commercially via the site's pharmacy. AbbVie will provide cytarabine as a labeled investigational product to sites who do not supply their own commercially available cytarabine.

Identity of Non-Investigational Product(s)

Sites may be responsible for obtaining cytarabine. For operational or regulatory purposes, Abbvie may provide non-investigational products depending on local requirements. Cytarabine should be obtained from a licensed pharmacy or wholesaler.

Each site will be responsible for maintaining drug accountability records including product description, manufacturer, and/or lot numbers for all non-investigational products dispensed by the site.

5.5.2.1 Packaging and Labeling

Venetoclax tablets or placebo for venetoclax tablets will be packaged in high density polyethylene (HDPE) plastic bottles. Each bottle of the venetoclax 50 mg tablets or placebo for venetoclax 50 mg tablets will contain 28 tablets. Each bottle of the venetoclax 10 mg tablets or placebo for venetoclax will contain 5 tablets. Each bottle of the venetoclax 100 mg tablets or placebo for venetoclax 100 mg tablets will contain 186 tablets. All bottles will be labeled per local regulatory requirements.

LDAC will be provided as 20 mg/ml per single use vial. Each vial and carton will be labeled per local regulatory requirements. Each vial must be administered per the applicable US prescribing information (USPI), Summary of Product Characteristics (SmPC) or local label.

5.5.2.2 Storage and Disposition of Study Drug(s)

Venetoclax or placebo for venetoclax study drug must be stored at 15° to 25°C (59° to 77°F). LDAC must be stored between 15° to 25°C (59° to 77°F). The investigational products are for investigational use only and are to be used only within the context of this study. The study drug supplied for this study must be maintained under adequate security and stored under the conditions specified on the label until dispensed for subject use or returned to AbbVie.

5.5.3 Method of Assigning Subjects to Treatment Groups

The IRT will randomize subjects into the 2 treatment arms in a 2:1 ratio (venetoclax + LDAC or placebo + LDAC). A bottle (kit) number randomization schedule and a subject randomization schedule will be generated by the Clinical Statistics Department at AbbVie prior to the start of the study. A copy of all randomization schedules will be kept by the Clinical Statistics Department at AbbVie and a copy will be forwarded to the IRT vendor.

Subject randomization will be stratified by AML status (secondary, de novo), age (18 – < 75, ≥ 75) and region (US, EU, China, Japan, Rest of world).

5.5.4 Selection and Timing of Dose for Each Subject

Venetoclax/placebo will be administered orally once daily (QD) Days 1 through 28, of a 28-day cycle, with a designated dose of 600 mg daily after ramp up in Cycle 1. During Cycle 1 Days 1 – 4, the dose will ramp up from 100 mg on Day 1, 200 mg on Day 2, 400 mg on Day 3 and 600 mg on Day 4.

Each dose of venetoclax/placebo should be taken with approximately 240 mL of water within 30 minutes after the completion of a meal, preferably breakfast. LDAC (20 mg/m²) should be given QD following administration of venetoclax or placebo on Days 1 – 10 of every cycle.

